3.1 Primary Objective

Aim 1 will test if African ancestry (%AF) is associated with short SWS duration and poor SWA in older AAs. **Challenge:** AAs consistently spend less time in SWS than whites²³⁻³². Although SWS shows significant heritability, social stressors may moderate these differences. **Approach:** test whether %AF⁴⁰ is associated with SWS characteristics after controlling for psychosocial factors (*e.g.* stress related to ethnicity). **Outcome:** positive results would suggest that racial differences in SWS have genetic underpinnings.

Aim 2 will test the effect of race and its interaction with baseline short SWS duration/poor SWA on longitudinal amyloid deposition. **Challenge:** AAs spend less time in SWS²³⁻³², a sleep stage important for A β dynamics⁴¹⁻⁴³ that may confer protection against amyloid deposition⁴⁴. **Approach:** assess how race is associated with longitudinal PiB uptake and its interaction with short SWS duration and poor SWA, after controlling for: 1) medial prefrontal (mPFC) atrophy, TST, AHI4% and cerebrovascular damage (measured as white matter lesion [WML] volume and abnormal diffusion kurtosis imaging [DKI] indices); and, 2) psychosocial factors, health care behaviors and medical morbidity. **Outcome:** reduced SWS/SWA would become a novel risk factor for AD in African Americans (AAs).

Aim 3 will test the effect of race and baseline poor SWA on cognition. **Challenge:** race and poor sleep have been associated with cognitive impairment. However, most studies are confounded by the inclusion of OSA patients, subjective measurements of sleep, lack of valid cognitive assessments for AAs and inadequate enrollment of minorities. **Approach:** we will test for the association between race and longitudinal changes in global cognition, memory, executive function and a sleep-dependent spatial navigational memory task. In addition, we will test their interaction with baseline SWA, using a similar approach as in Aim 2. **Outcome:** positive results would emphasize the importance of health messages promoting good sleep hygiene among AA elderly.

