9.1 Study Hypotheses

1. Hypothesis 1.1: poor SWS characteristics (short SWS duration, low %SWS, low relative SWA, low SWS continuity and high AI) at baseline will be associated with high %AF. Hypothesis 1.2: psychosocial factors (*e.g.* perceived discrimination) will partially moderate the above relationships.
2. Hypothesis 2.1: race will be associated with longitudinal increases in the annual rate of AD_{PiB}mask change. Hypothesis 2.2: the effect of race in terms of longitudinal increases in AD_{PiB}mask will be partially explained by poor relative SWA at baseline.
3. Hypothesis 3.1: race will be associated with longitudinal changes in global cognition, memory, executive function and sleep-dependent spatial navigational memory. Hypothesis 3.2: the association of race in terms of cognitive decline will be partially explained by poor relative SWA at baseline. Exploratory Hypothesis: absence of improvement in sleep dependent memory consolidation at baseline will be associated with longitudinal decreases in global cognition, memory and executive function.

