9.3 Statistical Methods

General considerations: we will incorporate standard techniques such as omnibus tests and appropriate adjustments to significance (α) levels (*e.g.*, Bonferroni correction) for *post-hoc* contrasts to control for multiple comparisons. Both selection and attrition biases might occur. Appropriate techniques (*e.g.*, Heckman 2-stage approach (GEE Probit Model)^{254;255} and Monte Carlo (EM algorithm)²⁵⁶ will be used to address biases or missing data. Attributes of those who withdrew to follow-up will be contrasted with completers to determine sources of attrition biases. Since only two time points will be analyzed, we will use linear regression models with the annual rate of amyloid change as dependent variable. Significance will be defined by $p < .05$ where p will be Bonferroni corrected when testing *post-hoc* contrasts.

- **Hypothesis (1)**: H1.1) for %AF associations, linear regression models, with each of SWS characteristics as the dependent variable, will be regressed on %AF controlling for age, sex, BMI, AHI, TST, sleep efficiency and WASO. H1.2) This model will test interaction by including the best SWS predictor as dependent variable, the psychosocial factor as a classification factor, %AF and the term created as the cross product of psychosocial factors and %AF.
- **Hypothesis 2-3 (H2-3)**: First we will calculate the associations between race and AD_{PiB}mask represented both as binary (AA *vs.* white) and numeric (%AF). Further analyses will use the representation (s) of race significantly associated with amyloid burden. Second, we will use hierarchical

CONFIDENTIAL

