linear regression, with rate of change of AD_{PiB}mask as the dependent variable and race as independent, adjusting for the matching factors: age, sex, BMI, education and annual income (block 1); ApoE4 and ABCA7 (block 2); DWML volumes, DKI indices and mPFC volume (block 3); and SWS characteristic (*e.g.* relative SWA) (block 4). Other covariates (*e.g.*, psychosocial) will be included in the final models if significantly different between AAs and whites as indicated by unequal variance t tests. Although we anticipate that relative SWA will be the best predictor of longitudinal change in AD_{PiB}mask, the best fitting model will be then replicated with each of the other SWS characteristics not listed before. On a final step, we will test whether the effect of SWS on amyloid deposition is different (*i.e.*, stronger) among AAs. The model would include AD_{PiB}mask change, the binary indicator of race (AA=1 *vs.* white=0) and SWA as described in H1.2. If the interaction is significant, it will imply that the effect of SWA on amyloid varies as a function of race. The sign of the estimated coefficient for this term would indicate whether SWA has a significantly stronger or weaker effect among AA. Exploratory Hypothesis: cognitive z-score change in subjects that show improvement in maze CT will be compared with those that don't show improvement using ANCOVA controlling for age, sex, BMI, race, education and ApoE4 status.

- **Post-hoc analyses**: a subset of *post-hoc* analyses will be performed by controlling by PiB levels at baseline and by splitting the sample into PiB+ and PiB- at baseline and performing a separate analysis for each subset. Stratified analyses will also be performed for men and women, as well as for AAs and whites. In addition, we will formally test the impact of PiB status (defined as PiB SUVR \geq 1.4) on the association of sleep measures with longitudinal increases in AD_{PiB}mask. Although we do not anticipate that sleep or SWS characteristics will change over the follow-up period, *post-hoc* analyses will be performed by assessing longitudinal changes in the sleep measures as correlates and predictors of longitudinal changes in the outcomes measures, using paired sample t-tests to assess the change in outcomes and sleep.

10 Source Documents and Access to Source Data/Documents

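### The race coding for the Hypothesis 2-3 models is chosen by its significance for amyloid burden; it should be fixed in advance

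*Combined protocol and SAP*

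**What the plan says.** Section 9.3, in the item for Hypotheses 2 and 3, first relates race to the AD_PiB mask index in two codings: binary (AA or white) and numeric (%AF). It then states: "Further analyses will use the representation (s) of race significantly associated with amyloid burden". The next step is the main model, a hierarchical regression that takes the rate of mask change "as the dependent variable and race as independent, adjusting for the matching factors". That outcome is the primary endpoint in the Protocol Summary. The last step, the race-by-SWA interaction, always uses the binary coding ("the binary indicator of race (AA=1", white=0).

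The hypotheses and aims set no such condition:

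- H2.1 (Section 9.1): "race will be associated with longitudinal increases in the annual rate of" mask change.
- H3.1 (Section 9.1): "race will be associated with longitudinal changes in global cognition, memory, executive function and sleep-dependent spatial navigational memory".
- Aim 2 (Section 3.1) will "assess how race is associated with longitudinal PiB uptake and its interaction with short SWS duration and poor SWA".
- Aim 3 (Section 3.1): "we will test for the association between race and longitudinal changes in global cognition, memory, executive function and a sleep-dependent spatial navigational memory task".

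Section 2.2 says that both codings will be used, again without a condition. The significance level is 0.05, and the Bonferroni correction applies to post-hoc contrasts only, so no multiplicity rule covers the two first-step tests.

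**The concern.** The main exposure for the primary endpoint should not depend on a p value. Under the rule as written, three things cannot be read from the plan:

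1. which coding enters the main model if neither is significant;
2. which coding leads if both are;
3. whether the first-step outcome is baseline level or annual change. If it is change, H2.1 has already been tested there, in both codings.

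Two consequences follow. Because the rule stands under a joint heading for Hypotheses 2 and 3, the race term for cognition is screened on a different outcome, amyloid. And if only %AF passes, the main model and the interaction step use different exposures. Binary race in the interaction step is not a defect in itself; the possible mismatch is.

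What is at stake is a clearly identified planned race estimate and, on the strictest reading, the power for H2.1 and H3.1.

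**Working it through.** **1. The plan's own figure.** Section 9.2 gives 150 AA and 60 white participants, baseline PiB CVs of 35% and 25%, and 80% (90%) power for a 13% (15%) higher mean in AAs. Set the white mean to 1, take SD = CV × group mean, and use a two-sided unequal-variance z-test at 0.05:

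- 13%: SE = √[(0.35×1.13)²/150 + 0.25²/60] = 0.0457; 0.13/0.0457 = 2.85; power = Φ(2.85 − 1.96) = 81.3%.
- 15%: SE = 0.0461; 0.15/0.0461 = 3.26; power = Φ(3.26 − 1.96) = 90.3%.

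Both figures reproduce. At the planned 13% difference, binary race therefore misses a baseline screen in about 19% of studies. At half of it (6.5%), SE = 0.0444, 0.065/0.0444 = 1.47, and binary race passes in only 31%.

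**2. Direct test of race on change.** The plan states no power for this, so an effect is assumed. The 200 completers in the 150:60 ratio give 143 and 57. With an assumed 0.44 SD effect, SE = √(1/143 + 1/57) = 0.1566; 0.44/0.1566 = 2.81; power is about 80%.

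**3. How alike the codings are.** Assume %AF has mean 80 and SD 12 in AAs and is near 1 in whites. Between-group variance = 0.715 × 0.285 × 79² ≈ 1,272; within-group variance ≈ 0.715 × 12² ≈ 103; correlation = √(1,272/1,375) ≈ 0.96.

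**4. Screen on baseline level.** Simulation: 20,000 replicates per scenario, unadjusted models, robust-variance screen, baseline-change correlation 0 or 0.3. The strict gate admits either coding and has no fallback. Its ranges cover taking binary when both pass, or counting any admitted coding.

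| True baseline difference | Binary passes | Either passes | Only %AF passes | Power, strict gate | Power, binary fallback |
|---|---|---|---|---|---|
| 13% | 0.81 | 0.83 | 0.02 | 0.66-0.70 | 0.79-0.80 |
| 6.5% | 0.31 | 0.34-0.35 | 0.03-0.04 | 0.27-0.30 | 0.80 |
| 0% | 0.05 | 0.06-0.07 | 0.01-0.02 | 0.05 | 0.80 |

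Check at correlation 0: 0.83 × 0.80 = 0.66.

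Variants of the strict gate, in the same order of baseline difference:

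- %AF SD from 8 to 20: 0.66-0.70, 0.26-0.31, 0.04-0.06.
- Pooled-variance screen: 0.57-0.60, 0.18-0.21, about 0.03.
- A cognitive outcome gated on baseline amyloid (assumed correlation 0 or −0.2): 0.66-0.68, 0.27-0.29, 0.05.

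Type I error for change under the strict gate is 0.003-0.049, so it is not inflated.

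**5. Screen on change.** With no race effect, at least one coding is significant in 5.7%, 6.2% and 6.7% of 40,000 runs for %AF SD 8, 12 and 20. The ceiling for two independent tests is 1 − 0.95² = 9.75%.

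**6. The undefined case.** If race is unrelated to burden, neither coding passes in about 93-94% of runs (1 minus 0.06-0.07). The plan then names no coding for the main model, just when a clear null estimate is wanted.

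**The case against.** The strongest reply is that the sentence chooses a coding and is not a gate. Section 9.3 calculates both associations and then goes on to the regression without an if; Aims 2-3 and Section 2.2 also commit to race models. The general considerations in the same section say "we will use linear regression models with the annual rate of amyloid change as dependent variable". If that governs the first step, H2.1 is tested there unconditionally in both codings, and the screen only decides what is carried into the adjusted models. The cognitive part rests on the joint heading, since the model sentences name only amyloid. With codings correlated at about 0.96, the choice between them hardly matters, and the large power losses need the least favourable reading plus inputs that the plan does not give.

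Most of this stands, and it limits the size of the point. The coding-choice reading is reasonable, and on it little or no power is lost. But no fallback and no lead coding are written. The term amyloid burden, together with the baseline PiB power in Section 9.2, keeps the baseline reading open. The heading does place cognition under the rule. Even on the mildest reading, a p value still selects the main exposure.

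**Conclusion.** The concern holds. The plan states a significance-driven rule for the exposure in its primary-endpoint model, at odds with unconditional hypotheses and aims, and leaves the outcome of that rule undefined in its most likely null case. The practical harm runs from almost none (binary fallback: 79-80% power; screen on change: about 6-7% type I error) to substantial (strict baseline gate: 66-70%, 27-30% or about 5% power, depending on the true baseline difference). The mismatch with the interaction step arises in about 1-4% of runs.

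The power figures rest on the assumed 0.44 SD effect, %AF distribution and baseline-change correlation, and on unadjusted models. The textual conflict and the missing rules do not. This should be fixed as a cheap improvement; it is not an error that invalidates the plan.

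**What to change.** Replace the selection sentence in Section 9.3 with: *The H2 and H3 models will be fitted whatever the association of race with amyloid burden, with the race coding(s) fixed in advance.* Then choose one of the following before analysis:

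- **One primary coding, the other reported as secondary.** Binary would match recruitment, group balancing and the interaction step; %AF would match the ancestry focus stated in the Protocol Summary. The cost is that one coding becomes secondary although the Protocol Summary and Section 2.2 give both standing.
- **Both codings with a stated multiplicity correction.** At 0.025 each, power to detect the assumed 0.44 SD effect with either coding is about 73-74% instead of 80%. Type I error is 0.031-0.035, because the codings are nearly collinear and the correction is conservative.

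The choice belongs to the investigators. Also state whether the first-step AD_PiB mask is baseline level or annual change. The change takes one or two sentences and no new data.

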On NPSG N2, participants will be trained in our published 3-D virtual maze spatial navigational test (see Figure 10)^{141;156}. Navigational memory represents a good model to study the effects of sleep-dependent memory consolidation. Rodent studies show that patterns of firing in hippocampal place cells during wake are replayed both in REM²²⁸ and NREM²²⁹ sleep. Behaviorally, sharp-wave ripple suppression impairs performance on a radial arm maze,²³⁰ while REM suppression impairs memory in the radial arm maze²³¹ and in the Morris water maze²³². In humans, overnight sleep enhances virtual maze navigation performance^{233;234}, while we have shown that maze completion time (CT) is attenuated after REM disruption¹⁷⁶ and is correlated with SWA in elderly subjects¹⁸⁸. Subjects will experience two different mazes at baseline and at the 2.5-year follow-up, and mazes will be counterbalanced across subjects for which maze is experienced first. Both mazes have been designed such that optimal CT is equivalent assuming perfect knowledge of the maze layout. Maze performance will be expressed as % change across sleep in maze CT compared to baseline CT before sleep. We have chosen a maze over a word-pair test^{105;235;236} because: 1) it taxes the hippocampus (more than a word-pair tasks would); 2) it's ecologically relevant to AD (*i.e.* spatial disorientation is one of the early clinical AD-symptoms); and 3) there are equivalent rodent models that lend insight into the underlying electrophysiological mechanisms (*i.e.* sharp-wave ripples, which cannot be captured with surface EEG).

Figure 10. Bird's eye view of virtual maze

PiB PET and MRI scans:

On visit 4, baseline and follow-up subjects will receive a single dose of 11.12 mCi PiB and perform a dynamic 60 min amyloid PiB PET-MR scan 35 min after injection.. The radioactive drug (PiB) shall meet appropriate chemical, pharmaceutical, and radionuclidic standards. The dose will be radioassayed proper to administration to ensure dosimetry data is correct. Further, the mass of the PiB is not expected to produce a pharmacologic response. PET/MR scans will be performed on an integrated 3T PET/MR

CONFIDENTIAL

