9.2 Sample Size Determination

Power was assessed under the assumption that dropout replacement will allow complete data to be acquired from 200 subjects. Based on the existing literature²³⁻³², the coefficient of variation (CV) of SWS duration is anticipated to be as high as 90% among AA and 40% among whites. Baseline data from 150 AA and 60 whites will therefore provide 80% power at the 5% significance level to detect a mean SWS duration among whites that is at least 28% higher than among AA. Based on PD4, the CV of PiB uptake at baseline is anticipated to be as high as 35% among AA and 25% among whites, providing 80(90)% power at the 5% significance level to detect a mean PiB uptake among AAs that is at least 13%(15%) higher than in whites. For Aim 1, the study will have 80% power at the 5% significance level to detect correlations of magnitude $|r|=0.20$ (the study from Halder et al³⁹ showed an R^2 of 11, implying an even greater correlation of 0.33 can be expected in our study). The multivariable regression analysis will have 80% power to detect SWS characteristics that can explain 3% of the variance in the longitudinal change in AD_{PiB}mask (Aim 2) or cognition (Aim 3) after adjusting for covariates that together explain at least 25% of the variance in AD_{PiB}mask/cognition. The detectable effect of 3% variance explained, implies the study can detect partial correlations of magnitude 0.1 between SWS and the outcomes adjusted for the cofactors. It is noted that the power of the multivariable analyses will improve if the covariates explain >25% of the variance. The study will have 80% power to detect sleep measures that explain 10% of the variance in the AD_{PiB}mask ratio even if the covariates explain a negligible percentage of the variance.

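### The exploratory maze hypothesis is tested only as improved versus not improved, although the score is continuous; if the relation is graded, this loses about 36% (50/50 split) to 51% (80/20 split) of the information under normality and linearity.

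*Combined protocol and SAP*

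**What the plan says.** Section 6.1 (Sleep-dependent Neuropsychological Tests) sets the scale of the measure: "Maze performance will be expressed as % change across sleep in maze CT compared to baseline CT before sleep". That is a continuous quantity.

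Section 9.1 words the exploratory hypothesis as a state: "absence of improvement in sleep dependent memory consolidation at baseline will be associated with longitudinal decreases in global cognition, memory and executive function". Section 9.3 tests it in one sentence: "cognitive z-score change in subjects that show improvement in maze CT will be compared with those that don't show improvement". The method named there is an ANCOVA with six adjustment variables.

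The Protocol Summary lists the question as Secondary Objective 2.1. Sections 2.2, 3.2, 9.1 and 9.3 call it exploratory. The plan gives no threshold for improvement, no expected share improving, no distribution of maze change and no power statement for this analysis.

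**The concern.** Two groups treat a very small and a very large overnight gain as the same, and separate subjects just either side of the cut as if they differed in kind. If better consolidation goes with less decline in a graded way, the spread within each group carries information that the planned ANCOVA ignores.

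The choice also departs from the plan's handling of its other main predictors. In section 9.3, %AF and the SWS characteristics enter linear regressions as numbers, and race is represented both as binary and as numeric. Only the maze predictor is confined to two groups, although the percentage change will be derived anyway.

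At stake is the sensitivity of the single planned test of whether maze consolidation predicts decline in three cognitive scores. A null result from the split would be harder to interpret than it need be.

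**Working it through.** **Inputs**
- Complete subjects: 200. Section 9.2 assumes that "dropout replacement will allow complete data to be acquired from 200 subjects".
- Level: 5% (section 9.3). Sidedness is not stated; two-sided is assumed.
- Covariates: six (age, sex, BMI, race, education, ApoE4), from section 9.3.
- Effect size: none is stated for this analysis. The nearest figure in section 9.2 is 80% power for an SWS characteristic that explains 3% of the variance in amyloid or cognitive change, "after adjusting for covariates that together explain at least 25% of the variance". It is borrowed here as an illustration.
- Share improving: not stated. Splits from 50/50 to 80/20 are assumed, with 90/10 as a stress case.

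**Step 1. Reproduce the plan's nearest figure.** f² = 0.03/(1 − 0.25 − 0.03) = 0.0417, so the noncentrality is 200 × 0.0417 = 8.33. The 1-df F test then has power 0.82 (0.819 with anything from 0 to 15 covariates), in line with the stated 80%. The matching partial correlation is √(0.03/0.75) = 0.20. Section 9.2 describes it as 0.1; that is a separate matter, and 0.20 is used here because it follows from the 3% and 25%.

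**Step 2. Efficiency of a split.** For a normal predictor with a linear effect and a share p in one group, relative efficiency is φ(z_p)²/[p(1 − p)]:
- 50/50: 0.3989²/0.25 = 0.637
- 70/30: 0.3477²/0.21 = 0.576
- 80/20: 0.2800²/0.16 = 0.490
- 90/10: 0.1755²/0.09 = 0.342

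**Step 3. Power at a true partial correlation of 0.20.** The split reduces the correlation to 0.20 × √efficiency. Power is from the noncentral F with N = 200 and six covariates. The N for 80% power is [(1.960 + 0.842)/atanh(r)]² + 3.

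| Form of predictor | Information lost | r seen by the test | Effective N | Power | N for 80% power |
|---|---|---|---|---|---|
| Continuous | 0% | 0.200 | 200 | 82% | 194 |
| 50/50 split | 36% | 0.160 | 127 | 62% | 306 |
| 70/30 split | 42% | 0.152 | 115 | 58% | 339 |
| 80/20 split | 51% | 0.140 | 98 | 51% | 398 |
| 90/10 split | 66% | 0.117 | 68 | 38% | 571 |

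The Fisher z approximation agrees to within a point (81% for the continuous form; 62%, 57% and 51% for the first three splits).

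**Step 4. Sensitivity to shape.** Loss was computed by simulation as 1 − corr(x, split x)² for splits from 50/50 to 80/20: uniform 25–52%; skewed percentage change 37–53%; t with 5 df 46–55%; t with 3 df 60–64%. The direction is stable under linearity; the size is not.

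**The case against.** **The hypothesis is worded in binary terms.** Section 9.1 speaks of absence of improvement, and the objectives speak of loss of sleep-dependent memory. The two-group ANCOVA tests exactly that contrast. If the truth is a step at the cut, the split loses nothing, and a linear term would be the less efficient form: the correlation between score and split works the same way in both directions, so the linear term would have relative efficiency 0.637 at 50/50. This objection stands, and it is why the two-group comparison should be kept. It does not justify having only that comparison, since the documents give no evidence for a step.

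**The size rests on assumptions.** A reader might infer that the plan discards a known share of its information. It does not follow: share improving, normality and linearity are all assumed. A reader might also infer that a power claim has been contradicted. None was made for this analysis.

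**The zero cut-point is an inference.** Zero is the natural reading, but no threshold is given. Nor is there a reliability figure to show how many subjects near the cut would be misclassified, and measurement noise would weaken a continuous predictor too.

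**The continuous form is not free of problems.** Percentage change divides by pre-sleep CT, cannot fall below −100% and has no upper limit, so skew and high-leverage values are plausible. This stands, and the fix must deal with it.

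**Importance is limited.** The analysis is labelled exploratory. A reader might take it as the only content of the secondary objectives, but section 3.2 also lists a linked objective on confounding by mPFC atrophy, DWML and DKI.

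**Conclusion.** The concern holds as a conditional and modest one. A continuous measure is analysed for this hypothesis only as two groups, with no definition of improvement. Under a normal predictor and a linear relation, the loss is about 36% at 50/50, 42% at 70/30 and 51% at 80/20; other plausible shapes over the same splits give 25% to 64%. The power figures illustrate this at a borrowed partial correlation of 0.20 and do not correct any stated figure. The loss does not arise if the effect is a step at no improvement. The primary amyloid endpoint, Aim 1 and the main Aim 3 hypotheses (3.1 and 3.2) are unaffected.

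**What to change.** In section 9.3, under the exploratory hypothesis:
- Make overnight change in maze CT, kept continuous, the main predictor of cognitive z-score change, in the same model with age, sex, BMI, race, education and ApoE4.
- Pre-specify a linearity check (a quadratic or spline term) and the handling of skew and outliers, for example by using the log ratio of post-sleep to pre-sleep CT.
- Define 'improvement', including its cut-point, and report the share improving.
- Keep the improved versus not-improved ANCOVA as a secondary analysis that matches the wording of section 9.1.

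This takes a few sentences in the plan and needs no new data, visits or subjects. The cost is a functional-form and outlier-handling choice, which should be fixed before the follow-up cognitive data are analysed.
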